10.4.2. Attribution Definitions

Assessment of Causality

The causal relationship to study intervention is determined by the investigator. The following selection should be used to assess all AEs.

Related

There is a reasonable causal relationship between study intervention administration and the AE.

Not Related

There is not a reasonable causal relationship between study intervention administration and the AE.

The term "reasonable causal relationship" means there is evidence to support a causal relationship.

10.4.3. Severity Criteria

An assessment of severity grade will be made using the following general categorical descriptors:

Mild: Awareness of symptoms that are easily tolerated, causing minimal discomfort and not interfering with everyday activities.

Moderate: Sufficient discomfort is present to cause interference with normal activity.

Severe: Extreme distress, causing significant impairment of functioning or incapacitation. Prevents normal everyday activities.

The investigator should use clinical judgment in assessing the severity of events not directly experienced by the participant (eg, laboratory abnormalities).

10.4.4. Special Reporting Situations

Safety events of interest on a sponsor study intervention in an interventional study that may require expedited reporting or safety evaluation include, but are not limited to:

• Overdose of a sponsor study intervention

- Suspected abuse/misuse of a sponsor study intervention
- Accidental or occupational exposure to a sponsor study intervention
- Unexpected therapeutic or clinical benefit from use of a sponsor study intervention
- Medication error, intercepted medication error, or potential medication error involving a
 Johnson & Johnson medicinal product (with or without patient exposure to the Johnson &
 Johnson medicinal product, eg, product name confusion, product label confusion, intercepted
 prescribing or dispensing errors)
- Exposure to a sponsor study intervention from breastfeeding

Special reporting situations should be recorded in the CRF. Any special reporting situation that meets the criteria of an SAE should be recorded on the SAE page of the CRF.

10.4.5. Procedures

All Adverse Events

All AEs, regardless of seriousness, severity, or presumed relationship to study intervention, must be recorded using medical terminology in the source document and the CRF. Whenever possible, diagnoses should be given when signs and symptoms are due to a common etiology (eg, cough, runny nose, sneezing, sore throat, and head congestion should be reported as "upper respiratory infection"). Investigators must record in the CRF their opinion concerning the relationship of the AE to study therapy. All measures required for AE management must be recorded in the source document and reported according to sponsor instructions.

For all studies with an outpatient phase, including open-label studies, the participant must be provided with a "wallet (study) card" and instructed to carry this card with them for the duration of the study indicating the following:

- Study number
- Statement, in the local language(s), that the participant is participating in a clinical study
- Investigator's name and 24-hour contact telephone number
- Local sponsor's name and 24-hour contact telephone number (for medical personnel only)
- Site number
- Participant number
- Any other information that is required to do an emergency breaking of the blind

Serious Adverse Events

All SAEs that have not resolved by the end of the study, or that have not resolved upon the participant's discontinuation from the study, must be followed until any of the following occurs:

- The event resolves
- The event stabilizes

- The event returns to baseline, if a baseline value/status is available
- The event can be attributed to agents other than the study intervention or to factors unrelated to study conduct
- It becomes unlikely that any additional information can be obtained (participant or health care practitioner refusal to provide additional information, lost to follow-up after demonstration of due diligence with follow-up efforts)

Any event requiring hospitalization (or prolongation of hospitalization) that occurs during participation in the study must be reported as an SAE, except hospitalizations for the following:

- Hospitalizations not intended to treat an acute illness or AE (eg, social reasons such as pending placement in long-term care facility)
- Surgery or procedure planned before entry into the study (must be documented in the eCRF). Note: Hospitalizations that were planned before the signing of the ICF, and where the underlying condition for which the hospitalization was planned has not worsened, will not be considered SAEs. Any AE that results in a prolongation of the originally planned hospitalization is to be reported as a new SAE.

The cause of death of a participant in a study within 12 weeks of the last dose of study intervention, whether or not the event is expected or associated with the study intervention, is considered an SAE.

Information regarding SAEs will be transmitted to the sponsor using an SAE reporting form, which must be completed and signed by a physician from the study site, and transmitted in a secure manner to the sponsor within 24 hours. The initial and follow-up reports of an SAE should be made by facsimile (fax). Telephone reporting should be the exception and the reporter should be asked to complete the appropriate form(s) first.

10.4.6. Product Quality Complaint Handling

Definition

A product quality complaint (PQC) is defined as any suspicion of a product defect related to manufacturing, labeling, or packaging, ie, any dissatisfaction relative to the identity, quality, durability, reliability, or performance of a distributed product, including its labeling, drug delivery system, or package integrity. A PQC may have an impact on the safety and efficacy of the product. In addition, it includes any technical complaints, defined as any complaint that indicates a potential quality issue during manufacturing, packaging, release testing, stability monitoring, dose preparation, storage or distribution of the product or the drug delivery system.

This definition includes any PQC related to a device constituent in a combination product, including those used in the administration of the study intervention or the comparator. A device deficiency is an inadequacy of a device with respect to its identity, quality, durability, reliability,

safety, or performance. Device deficiencies include malfunctions, use errors, and inadequate labeling.

Procedures

All initial PQCs must be reported to the sponsor by the study site personnel within 24 hours after being made aware of the event.

A sample of the suspected product should be maintained under the correct storage conditions until a shipment request is received from the sponsor.

10.4.7. Contacting Sponsor Regarding Safety, Including Product Quality

The names (and corresponding telephone numbers) of the individuals who should be contacted regarding safety issues, PQC, or questions regarding the study are listed in the Protocol Supplementary Information, which will be provided as a separate document.

10.5. Appendix 5: Contraceptive and Barrier Guidance

Participants must follow contraceptive measures as outlined in Section 5.1, Inclusion Criteria. Pregnancy information will be collected and reported as noted in Section 8.3.5, Pregnancy and Appendix 4: Adverse Events, Serious Adverse Events, Product Quality Complaints, and Other Safety Reporting: Definitions and Procedures for Recording, Evaluating, Follow-up, and Reporting.

Definitions

Woman of Childbearing Potential (WOCBP)

A woman is considered fertile following menarche and until becoming postmenopausal unless permanently sterile (see below).

Woman Not of Childbearing Potential

premenarchal

A premenarchal state is one in which menarche has not yet occurred.

postmenopausal

A postmenopausal state is defined as no menses for 12 months without an alternative medical cause. A high follicle stimulating hormone (FSH) level (>40 IU/L or mIU/mL) in the postmenopausal range may be used to confirm a postmenopausal state in women not using hormonal contraception or hormonal replacement therapy (HRT), however in the absence of 12 months of amenorrhea, a single FSH measurement is insufficient. If there is a question about menopausal status in women on HRT, the woman will be required to use one of the non-estrogen-containing hormonal highly effective contraceptive methods if she wishes to continue HRT during the study.

• permanently sterile (for the purpose of this study)

Permanent sterilization methods include hysterectomy, bilateral salpingectomy, and bilateral oophorectomy.

Note: If the childbearing potential changes after start of the study (eg, a premenarchal woman experiences menarche) or the risk of pregnancy changes (eg, a woman who is not heterosexually active becomes active), a woman must begin a highly effective method of contraception, as described throughout the inclusion criteria.

Contraceptive (birth control) use by men or women should be consistent with local regulations regarding the acceptable methods of contraception for those participating in clinical studies.

Typical use failure rates may differ from those when used consistently and correctly.

Examples of Contraceptives

EXAMPLES OF CONTRACEPTIVES^a ALLOWED DURING THE STUDY INCLUDE:

USER INDEPENDENT

Highly Effective Methods That Are User Independent *Failure rate of* <1% *per year when used consistently and correctly.*

- Intrauterine device (IUD)
- Intrauterine hormone-releasing system (IUS)
- Bilateral tubal occlusion
- Azoospermic partner (vasectomized or due to medical cause)

(Vasectomized partner is a highly effective contraceptive method provided that the partner is the sole sexual partner of the woman of childbearing potential and the absence of sperm has been confirmed. If not, additional highly effective method of contraception should be used. Spermatogenesis cycle is approximately 74 days.)

USER DEPENDENT

Highly Effective Methods That Are User Dependent *Failure rate of* < 1% *per year when used consistently and correctly.*

 Combined (estrogen- and progestogen-containing) hormonal contraception associated with inhibition of ovulation^b

oral

Sexual abstinence

(Sexual abstinence is considered a highly effective method only if defined as refraining from heterosexual intercourse during the entire period of risk associated with the study intervention. The reliability of sexual abstinence needs to be evaluated in relation to the duration of the study and the preferred and usual lifestyle of the participant.)

NOT ALLOWED AS SOLE METHOD OF CONTRACEPTION DURING THE STUDY (not considered to be highly effective - failure rate of ≥1% per year)

[figure not shown]
- Progestogen-only oral hormonal contraception where inhibition of ovulation is not the primary mode of action.
- Male condom with or without spermicide
- Periodic abstinence (calendar, symptothermal, post-ovulation methods)
- Withdrawal (coitus-interruptus)
- Lactational amenorrhea method (LAM)
- a) Typical use failure rates may differ from those when used consistently and correctly.
- b) Hormonal contraception may be susceptible to interaction with the study intervention, which may reduce the efficacy of the contraceptive method. In addition, consider if the hormonal contraception may interact with the study intervention.

10.6. Appendix 6: Liver Safety: Suggested Actions and Follow-up Assessments

A. STOPPING ALGORITHM

Study intervention will be discontinued for a participant if liver chemistry stopping criteria are met.

Phase 2 Liver Chemistry Stopping Criteria and Increased Monitoring Algorithm

Abbreviations: ALT = alanine transaminase; AST = aspartate transaminase, INR = international normalized ratio; SAE = serious adverse event; ULN = upper limit of normal, Tbili = Total bilirubin.

B. FOLLOW-UP ASSESSMENTS

Phase 2 liver chemistry stopping criteria are designed to assure participant safety and to evaluate liver event etiology.

Phase 2 Liver Chemistry Stopping Criteria and Follow-up Assessments

Liver Chemistry Stopping Criteria and Fonow-up Assessments				
4 T FD 4 GFD	Liver Chemistry Stopping Criteria			
ALT or AST- absolute	ALT or AST ≥5xULN			
ALT or AST	ALT on ACT >2 will Ni nomicto fon >4 woods			
Increase	ALT or AST ≥3xULN persists for ≥4 weeks			
Bilirubin ^{1,2}	ALT or AST ≥3xULN and to	otal bilirubin ≥2xULN (>35% direct bilirubin)		
INR ²	ALT or AST ≥3xULN and in	nternational normalized ratio (INR) >1.5		
Cannot Monitor	ALT or AST≥3xULN and ca	nnot be monitored weekly for 4 weeks		
Symptomatic ³	ALT or AST ≥3xULN assoc	iated with symptoms (new or worsening)		
	believed to be related to liver	r injury or hypersensitivity		
Su	ggested Actions, Monitoring	, and Follow-up Assessments		
	Actions	Follow-up Assessments		
• Immediately di	scontinue study intervention	• Viral hepatitis serology ⁴		
24 hours	t to the sponsor within	• Obtain blood sample for pharmacokinetic (PK) analysis approximately 60 minutes after the most recent dose ⁵		
 Complete the liver event/expedited reporting form, and complete an SAE CRF if the event also met the criteria for an SAE² Perform follow-up assessments as described in the Follow-up Assessment column. 		Obtain serum creatine phosphokinase (CPK), lactate dehydrogenase (LDH), gamma-glutamyltransferase (GGT), glutamate dehydrogenase (GLDH), and serum albumin		
Monitor the participant until liver chemistry test abnormalities resolve, stabilize, or return to baseline		 Fractionate bilirubin, if total bilirubin ≥2xULN 		
MONITORING:		Obtain complete blood count with		
If ALT or AST ≥3	SXULN AND total bilirubin	differential to assess eosinophilia		
≥2xULN or INR >1.5: • Repeat liver chemistry tests (include ALT, aspartate transaminase [AST], alkaline phosphatase, total bilirubin, and INR) and		Record the appearance or worsening of clinical symptoms of liver injury, or hypersensitivity, on the liver event/expedited reporting form		
 perform liver event follow-up assessments within 24 hours Monitor participant twice weekly until liver chemistry test abnormalities resolve, stabilize, or return to baseline 		Record use of concomitant medications (including acetaminophen, herbal remedies, and other over-the-counter medications) on the concomitant medications CRF		
 A hepatology consultation is recommended If ALT or AST≥3xULN AND total bilirubin <2xULN and INR ≤1.5: 				

CONFIDENTIAL – FOIA Exemptions Apply in U.S.

- Repeat liver chemistry tests (include ALT, AST, alkaline phosphatase, total bilirubin and INR) and perform liver chemistry follow-up assessments within 24 to 72 hours
- Monitor participants weekly until liver chemistry abnormalities resolve, stabilize, or return to baseline
- **Do not restart/rechallenge** participant with study intervention unless allowed per protocol and sponsor approval is granted

If ALT or AST≥3xULN AND total bilirubin ≥2xULN or INR >1.5 obtain the following in addition to the assessments listed above:

- Anti-nuclear antibody, anti-smooth muscle antibody, Type 1 anti-liver kidney microsomal antibodies, and quantitative total immunoglobulin G (IgG) or gamma globulins
- Serum acetaminophen adduct assay, when available, to assess potential acetaminophen contribution to liver injury in participants with definite or likely acetaminophen use in the preceding week
- Liver imaging (ultrasound, magnetic resonance, or computerized tomography) to evaluate liver disease; complete liver imaging form
- Liver biopsy may be considered and discussed with local specialist if available, for instance:

In participants when serology raises the possibility of autoimmune hepatitis (AIH)

In participants when suspected drug-induced liver injury (DILI) progresses or fails to resolve on withdrawal of study intervention

In participants with acute or chronic atypical presentation

- If liver biopsy conducted complete liver biopsy form
- Serum bilirubin fractionation should be performed if testing is available. If serum bilirubin fractionation is not immediately available, discontinue study intervention if ALT or AST ≥3xULN and total bilirubin ≥2xULN. Additionally, if serum bilirubin fractionation testing is unavailable, record the absence/presence of detectable urinary bilirubin on dipstick which is indicative of direct bilirubin elevations suggesting liver injury.
- 2. All events of ALT or AST ≥3xULN and total bilirubin ≥2xULN (>35% direct bilirubin) or ALT or AST ≥3xULN and INR >1.5 may indicate severe liver injury (possible 'Hy's Law') and must be reported to sponsor in an expedited manner and as an SAE if SAE criteria met (excluding studies of hepatic impairment or cirrhosis). The INR stated threshold value will not apply to participants receiving anticoagulants.
- 3. New or worsening symptoms believed to be related to liver injury (such as fatigue, nausea, vomiting, right upper quadrant pain or tenderness, or jaundice) or hypersensitivity (such as fever, rash or eosinophilia).
- 4. Includes HBsAg (HBV surface antigen), anti-HBs (HBV surface antibody), and anti-HBc total (HBV core antibody total). For participants who are eligible with negative HBsAg, and positive core antibody (anti-HBc) and/or surface antibody (anti-HBs), and negative HBV DNA test, HBV DNA quantitation should be monitored at least every 3 months or shorter.

5. PK sample may not be required for participants known to be receiving placebo or non-comparator interventions. Record the date/time of the PK blood sample draw and the date/time of the last dose of study intervention prior to the blood sample draw on the CRF. If the date or time of the last dose is unclear, provide the participant's best approximation. If the date/time of the last dose cannot be approximated OR a PK sample cannot be collected in the time period indicated above, do not obtain a PK sample. Instructions for sample handling and shipping are in the Investigational Product Procedures Manual (IPPM) and Investigational Product Procedure Instructions (IPPI).

10.7. Appendix 7: Hepatitis B Virus (HBV) Screening with HBV DNA Testing

Participants must undergo screening for hepatitis B virus (HBV). At a minimum, this includes testing for HBsAg (HBV surface antigen), anti-HBs (HBV surface antibody), and anti-HBc total (HBV core antibody total):

- Participants who test negative for all HBV screening tests (ie, HBsAg-, anti-HBc-, and anti-HBs-) are eligible for this protocol.
- Participants who test negative for surface antigen (HBsAg-) and test positive for core antibody (anti-HBc+) and surface antibody (anti-HBs+) are eligible for this protocol.
- Participants who test **positive only** for **surface antibody** (anti-HBs+) are eligible for this protocol.
- Participants who test **positive** for surface antigen (HBsAg+) are NOT eligible for this protocol, regardless of the results of other hepatitis B tests.
- Participants who test positive only for core antibody (anti-HBc+) must undergo further testing for the presence of hepatitis B virus deoxyribonucleic acid (HBV DNA) test. If the HBV DNA test is negative, the participant is eligible for this protocol. If the HBV DNA test is positive, the participant is NOT eligible for this protocol. In the event the HBV DNA test cannot be performed, the participant is NOT eligible for this protocol. For participants who are eligible with negative HBsAg, and positive core antibody (anti-HBc) and/or surface antibody (anti-HBs), and negative HBV DNA test, HBV DNA quantitation should be monitored at least every 3 months or shorter.

These eligibility criteria based on HBV test results are also represented in:

Table 4: Eligibility based on hepatitis B virus test results				
HE	PATITIS B TEST RESI	ULT		
Hepatitis B surface antigen (HBsAg)	Hepatitis B surface antibody (anti-HBs)	Hepatitis B core antibody (anti-HBc total)	STATUS	
Negative	negative	Negative		
Negative	(+)	Negative	Eligible	
Negative	(+)	(+)		
(+)	negative or (+)	negative or (+)	Not eligible	
Negative	negative	(+)	(Require testing for presence of HBV DNA*)	

^{*} If HBV DNA is detectable, the participant is not eligible for this protocol. If HBV DNA testing cannot be performed, or there is evidence of chronic liver disease, the participant is not eligible for the protocol.

For participants who are not eligible for this protocol due to HBV test results, consultation with a physician with expertise in the treatment of hepatitis B virus infection is recommended.

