Pharmacokinetics and																	
Immunogenicity																	
Serum guselkumab concentrationf		2X	2X	2X	X	X	X	X	X	X	X	X	X	X	X	X	X
Antibodies to guselkumab		X	X	X	X			X		X		X		X	X	X	X
Biomarkers																	
Serum biomarkers		X	X		X	X		X	X					X			X
PBMCs		X	X					X						X			X
Skin biopsy (optional)		X						X									
Pharmacogenomics (optional) ^d																	
Blood sample collection for DNA (EDTA tube)		X															
Blood sample collection for RNA (PAXgene tube)		X	X					X									

Abbreviations: CRP=C-reactive protein; DNA=deoxyribonucleic acid; ECG=electrocardiogram; EDTA= ethylenediaminetetraacetic acid; EOS= end-of-study; ET=early termination; FSSG= Frequency Scale for the Symptoms of Gastroesophageal reflux disease; HAQ-DI= Health Assessment Questionnaire-Disability Index; HIV= human immunodeficiency virus; HRCT= high resolution computed tomography; ICF=informed consent form; IGRA= interferon gamma release assays; LTE=

long-term extension, mRSS= modified Rodnan skin score; PBMC= Peripheral blood mononuclear cells; PRO=patient-reported outcome; RNA=ribonucleic acid; SoA=schedule of assessments

Footnotes:

- a. Must be signed before first study-related activity.
- b. Minimum criteria for the availability of documentation supporting the eligibility criteria will be described in the full protocol. Check clinical status again before first dose of study medication.
- c. All PRO assessments should be conducted before other assessments in the order listed in the above SoA table.
- d. The pharmacogenomic sample should be collected at the specified time points, but it may be collected at a later time point without constituting a protocol deviation.
- e. For participants who are eligible with surface antigen (HbsAg) negative, core antibody (anti-HBc) and/or surface antibody (anti-HBs) positive, and HBV DNA test is negative, HBV DNA quantitation should be monitored at least every 3 months or shorter.
- f. For all visits where study intervention will be administered, 1 blood sample should be collected prior to study intervention administration for evaluation of serum concentrations and/or antibodies to study intervention. In addition, for IV infusion-related visits (Week 0, 4, 8), another blood draw should be taken approximately 60 minutes after the completion of the IV infusion for serum concentration measurement.
- g. mRSS must be assessed by the same investigator longitudinally throughout the study

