2.3.1. Risks for Study Participation

Summary of Data/ Rationale for Risk	Mitigation Strategy
The benefit-risk of guselkumab in the treatment of SSc has not been established.	Participants will discontinue study intervention if it is not in their best interest or if they need to initiate protocol-prohibited medications including certain biologics (Section 6.8 and Section 7.1).
Risks Due to Study Intervention G	Guselkumab
Available animal and human data suggest that blockade of IL-23 may be associated with an increased infection risk.	 Participants with a history of, or ongoing, chronic or recurrent infectious disease, including human immunodeficiency virus (HIV), Hepatitis B or C, will be excluded from the study. Similarly, participants with evidence of active or untreated latent tuberculosis (TB) will be excluded from the study (Section 5.2). Participants who have received Bacille Calmette-Guérin (BCG) vaccination within 12 months or any other live viral or bacterial vaccination within 12 weeks from randomization will be excluded from the study. In addition, participants must agree not to receive a live viral or live bacterial vaccination during the study and for 12 weeks after receiving the last dose of study intervention. Participants will be instructed to seek medical attention if they develop signs or symptoms suggestive of an infection, and investigators are instructed in the protocol to monitor for signs
	or symptoms of infections, including TB (Section 8.2.9 and Section 8.2.10). • Discontinuation of a participant's study intervention must be strongly considered if the participant develops a
	Rationale for Risk The benefit-risk of guselkumab in the treatment of SSc has not been established. Risks Due to Study Intervention C Available animal and human data suggest that blockade of IL-23 may be associated with an increased

CONFIDENTIAL – FOIA Exemptions Apply in U.S.

		not limited to sepsis or
		pneumonia. In addition, any serious infection should be discussed with the medical monitor or designee, and study intervention should be withheld until the clinical assessment is complete (Section 8.2.10).

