	Crohn's disease program in a participant who received guselkumab 1200 mg intravenous (IV) at Weeks 0, 4, and 8, and 200 mg subcutaneous (SC) at Week 12. Based on the hepatocellular pattern of injury, temporal relationship of the event to guselkumab exposure, and the exclusion of alternative etiologies, this event may represent druginduced liver injury possibly related to guselkumab. Alanine aminotransferase (ALT)/ aspartate aminotransferase AST abnormailities are a known risk for guselkumab, and that in the psoriatic arthritis studies, patients receiving guselkumab every 4 weeks (Q4W) were more likely to experience transaminase elevations than those receiving it every 8 weeks (Q8W).	accordance with regulatory guidance (FDA 2009). In addition, the induction doses evaluated in this clinical program will not exceed 400 mg IV. • Participants with marked liver enzyme elevations or symptoms or signs of liver dysfunction (eg, jaundice), should undergo a thorough investigation for possible causes of liver injury. A participant must have their study intervention discontinued if the participant has severe liver test abnormalities that are not transient and are not explained by other etiologies (Section 7.1 and Section 10.6).
Immunosuppression	It is unknown if guselkumab in combination with other immunosuppressives increases the risk of diseases associated with immunosuppression, such as infections or malignancy.	• In order to minimize the theoretical increased risk of infection or malignancy with the combination of guselkumab with immunosuppressive therapy, the baseline dose of oral corticosteroids on study entry is limited ≤10 mg of prednisolone or equivalent per day which must be at a stable dose ≥4 weeks prior to first dose of study intervention. Furthermore, participants receiving investigational or approved immunomodulatory agents like IL-23 inhibitor therapy, IL-12/23 inhibitors, or IL-17 inhibitors, failed for efficacy in SSc or within 12 weeks or 5 half-lives

CONFIDENTIAL – FOIA Exemptions Apply in U.S.

27

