8. STUDY ASSESSMENTS AND PROCEDURES

Overview

The Schedule of Activities summarizes the frequency and timing of efficacy, PK, immunogenicity, PD, biomarker, pharmacogenomic, and safety measurements applicable to this study.

If multiple assessments are scheduled for the same timepoint, it is recommended that procedures be performed in the following sequence: ECG and vital signs (blood pressure, pulse rate, respiratory rate, and axillary body temperature) should be performed first, and then blood draws for PK or laboratory measurements. Urine and blood collections for PK and PD assessments should be kept as close to the specified time as possible. Other measurements may be done earlier than specified timepoints if needed. Actual dates and times of assessments will be recorded in the source documentation and eCRF.

For each participant, the maximum amount of blood drawn in this study will not exceed 567 mL through Week 112.

Repeat or unscheduled samples may be taken for safety reasons or for technical issues with the samples.

Table 3: Volume of Blood to be Collected from Each Participant

	** 1	N. 66 1	Approximate
	Volume per	No. of Samples	Total Volume of
Type of Sample	Sample (mL)	per Participant	Blood (mL) ^a
Safety (including screening and post-intervention			
assessments)			
- T-spot	10	1	10
- Hematology	2 - 3	26	52 - 78
- Serum chemistry	2.5	26	65
- Serology (HIV, HBV, HCV)	8.5	1	8.5
- HBV DNA testing	6	8	48
Pharmacokinetic/Immunogenicity samples	7.5	25	187.5
Pharmacodynamic/Biomarker samples			
- PBMCs	2×8	4	64
- Serum biomarkers	8.5	7	59.5
Autoantibodies	3	1	3
Pharmacogenomic sample ^b			
- EDTA	4 - 6	1	4 - 6
- Paxgene tube	5	3	15
Approximate Total ^c			516.5 – 544.5

Abbreviations: DNA=deoxyribonucleic acid; EDTA= ethylenediaminetetraacetic acid; HBV= hepatitis B virus; HCV= hepatitis C virus; HIV= human immunodeficiency virus; PBMC= peripheral blood mononuclear cells

a. Calculated as number of samples multiplied by amount of blood per sample.

b. A blood sample will be collected only from participants who have consented to provide an optional DNA and RNA samples for research.

c. Repeat or unscheduled samples may be taken for safety reasons or technical issues with the samples.

Screening

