8.2.11. Hepatitis B Monitoring

For participants who are eligible with surface antigen (HbsAg) negative, core antibody (anti HBc) and/or surface antibody (anti-HBs) positive, and HBV deoxy ribonucleic acid (DNA) test is negative, HBV DNA quantitation should be monitored at least every 3 months or shorter.

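### Participants positive for both anti-HBc and anti-HBs are admitted without an HBV DNA test, and the 3-monthly HBV DNA monitoring rule applies only after a negative test, so read literally they get neither

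*Protocol*

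**What the plan says.** Protocol Appendix 7 (Section 10.7) requires HBsAg, anti-HBs and total anti-HBc for everyone at screening, so every serology pattern can be identified. It then states that HBsAg-negative participants who are dual-positive may enter: "and test positive for core antibody (anti-HBc+) and surface antibody (anti-HBs+) are eligible for this protocol". Those positive for anti-HBs alone are also eligible outright. Only participants positive for anti-HBc alone must have an HBV DNA test, and they are excluded if it is positive or cannot be done. Table 4 agrees. The entry "Require testing for presence of HBV DNA" and its footnote belong to the isolated anti-HBc row, and the dual-positive row sits in the eligible block.

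The monitoring sentence later in Appendix 7 covers HBsAg-negative participants with "positive core antibody (anti-HBc) and/or surface antibody (anti-HBs), and negative HBV DNA test, HBV DNA quantitation should be monitored at least every 3 months". Section 8.2.11 sets the same condition: "test is negative, HBV DNA quantitation should be monitored at least every 3 months or shorter". So does footnote e to SoA Table 1: "HBV DNA test is negative, HBV DNA quantitation should be monitored at least every 3 months or shorter". The rule also appears in the synopsis, in footnote j to SoA Table 2 and in note 4 of Appendix 6, each time with a negative DNA test as a condition.

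**The concern.** The monitoring rule names dual-positive participants through its and/or wording and presupposes that they have a negative DNA result. The eligibility rule never asks for that result. The two rules fit together only for isolated anti-HBc positives.

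The stake is participant safety. The risk table in Section 2.3.1 answers the infection risk of IL-23 blockade by saying that participants with "chronic or recurrent infectious disease, including human immunodeficiency virus (HIV), Hepatitis B or C, will be excluded from the study". On combined treatment it says: "It is unknown if guselkumab in combination with other immunosuppressives increases the risk of diseases associated with immunosuppression, such as infections or malignancy". Section 6.8 allows stable oral corticosteroids, and after Week 24 it allows rescue with prednisolone up to 20 mg/day or azathioprine. For dual-positive participants the text neither establishes HBV DNA status before the first dose nor follows it afterwards.

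**Working it through.** **Eligibility against monitoring.** Each serology pattern in Appendix 7 and Table 4, set against the two rules as written:

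| HBsAg | anti-HBs | anti-HBc | Eligible | Screening DNA test ordered | Monitoring triggered |
|---|---|---|---|---|---|
| – | – | – | yes | no | no (not intended) |
| – | + | – | yes | no | no: named in the rule, but no DNA result |
| – | + | + | yes | no | no: named in the rule, but no DNA result |
| – | – | + | only if DNA negative | yes | yes |
| + | any | any | no | not applicable | not applicable |

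Isolated anti-HBc is the only pattern for which both the test and the monitoring are mandated.

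**Does other text order the test?**
- Exclusion criterion 14 excludes those who test positive for HBV infection but orders no DNA test.
- The screening list in Appendix 2 names HBsAg as its only HBV marker.
- SoA Table 1 has no HBV DNA row. The rule stands only in footnote e.
- Table 3 budgets 8 HBV DNA samples of 6 mL. That is a volume allowance, not an instruction to test.
- The liver work-up in Appendix 6 calls for HBV serology. Its DNA sentence again depends on an earlier negative DNA test.

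**Number affected.** The documents give no prevalence, so p is an assumption. With n = 56, the expected number is 56p and the chance of at least one is 1 − (1 − p)^56.

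| p | Expected number | Chance of at least one |
|---|---|---|
| 1% | 0.6 | 43% |
| 5% | 2.8 | 94% |
| 10% | 5.6 | 99.7% |
| 20% | 11.2 | over 99.9% |

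Under 1:1 allocation about half of these would receive guselkumab in the main study. All who enter the LTE would receive it.

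**Blood volume.** The Table 3 maximum is reproduced by 10 + 78 + 65 + 8.5 + 48 + 187.5 + 64 + 59.5 + 3 + 6 + 15 = 544.5 mL, which leaves 567 − 544.5 = 22.5 mL. The 8 budgeted HBV DNA samples equal one per 13 weeks over 104 weeks (104/13 = 8). If a screening test were one of them, the other 7 would cover 91 weeks, so a ninth may be needed: 544.5 + 6 = 550.5 mL, leaving 16.5 mL.

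The 413 mL in Section 4.2.1 is reproduced from the SoA Table 1 counts for a participant who does not enter the LTE, including the Week 60 visit:
- hematology 16 × 3 = 48
- chemistry 16 × 2.5 = 40
- PK 18 × 7.5 = 135
- HBV DNA 4 × 6 = 24
- all other samples 10 + 8.5 + 64 + 59.5 + 3 + 6 + 15 = 166

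The total is 48 + 40 + 135 + 24 + 166 = 413 mL. With a fifth HBV DNA sample it is 419 mL.

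**The case against.** The strongest reply is that nobody would read the text this way. If testing were meant only for isolated anti-HBc positives, the and/or reference to surface antibody would have no function. Footnote e is attached to the hepatitis serology row, which is marked only at screening. Appendix 7 has HBV DNA testing in its title and calls the three markers a minimum. Table 3 sets aside 8 DNA samples. On this view the sponsor intended to test and monitor dual-positive participants, and the defect is loose wording.

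As evidence of intent this stands, and nothing suggests a decision to leave these participants untested. It does not close the gap. Eligibility follows the written criteria, which admit them without condition, and a site that applied them exactly would commit no deviation, so monitoring visits would have nothing to flag.

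Some other points also stand:
- Corticosteroids are capped at a stable 10 mg/day outside rescue and short courses for non-SSc conditions. Other systemic immunosuppressives are prohibited, and azathioprine is optional rescue after an mRSS rise of at least 5.
- Real safeguards exist: AST and ALT at most 2 × ULN at entry, chemistry at every main-study visit, and liver stopping rules. They respond to raised enzymes and do not replace a DNA result.
- The documents do not quantify the risk carried by dual-positive status. The probabilities above concern enrolling a dual-positive participant, not one who is DNA-positive or harmed.

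**Conclusion.** The concern holds. As written, the protocol admits dual-positive participants with no HBV DNA test and makes their monitoring depend on a result that it never requests. Participants positive for anti-HBs alone fall into the same literal gap. Isolated anti-HBc positives and HBsAg positives are handled consistently. The textual mismatch is certain. How many people it touches is not, because that depends on the assumed prevalence: from fewer than 1 expected participant at 1% to about 11 at 20%. The matter is confined to eligibility and safety, with no effect on the primary analysis, power or error rate. It should be corrected because the eligibility rule defeats a safeguard that the sponsor wrote for these same participants.

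**What to change.** - In Appendix 7 and Table 4, require a negative HBV DNA test at screening for every HBsAg-negative, anti-HBc-positive participant, whatever the anti-HBs result. Exclude the participant if DNA is detected or the test cannot be done, as already written for isolated anti-HBc.
- For participants positive for anti-HBs alone, decide one way: add the same test, or remove them from the monitoring rule in all six places.
- Test any dual-positive participant already dosed without a result at the next visit, and start 3-monthly monitoring if negative.
- As a minor alignment, add anti-HBs, total anti-HBc and reflex HBV DNA to the Appendix 2 screening list.

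The cost is a protocol amendment with IEC/IRB approval, possibly the loss of a few DNA-positive candidates, and at most one extra 6 mL sample for some participants. That keeps within the Section 8 limit, under which "the maximum amount of blood drawn in this study will not exceed 567 mL through Week 112". The main-study figure in Section 4.2.1 may need to rise to 419 mL if the screening test is not already among the samples it counts.
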